8.0 PRIVACY AND CONFIDENTIALITY PROTECTIONS

Research procedures will be conducted in private areas and we are only collecting the minimum amount of information necessary to conduct the study. No sensitive data (HIV status, illicit drug use) will be collected. Identifiable records will only be available to study team members.

Data are not being shared outside of UW except through publications, in which case the data do not identify individual subjects. Study data will be managed by Drs. [name] and [name]. Data will not be placed on unencrypted laptop computers. Coded electronic data will be kept on the Obstetrics and Gynecology and Radiology Department secure network drives. A separate file linking codes to subject identity will be kept in the same manner, in a folder separate from study data. At the end of 7 years study data will be de-identified by destroying the link to identifiable

information. Until that time data will remain coded and the file linking codes to subject identity kept as well.

All imaging will be performed for research purposes only and will be given a unique study number that cannot be linked to the patients' medical records in any way. Imaging research images will be stored on PACS under this study number only. The investigators will have access to the patients' electronic medical records that are relevant to this study. Study records will be kept for seven years. Study data will be managed by the PI and co-PI.

Subject's identifiable information will be linked to a study code. The study code will be used to identify the subject and research images. Research images may be used in scientific presentations, but all images will be de-identified. The data will be stored on the Principal Investigator's (PI or co-PI) password protected computer in her locked office. The code will be stored separate from the data on the PI's computer in her locked office.

9.0 DATA AND SAFETY MONITORING

Safety monitoring of research protocols investigating novel PET tracers utilize a combination of tools. These are framed to provide adequate clinical trial oversight ensuring that the research team is complying with the conditions of IRB approval and FDA requirements. The tools enable frequent evaluations of study-related activities, identification of deviations or noncompliance with the conduct of the study or protocol, review of adverse events tracking and reporting, and review of drug production and accountability.

These tools include:

- Study visit checklists – Research Coordinators use study visit checklists to ensure that all study required procedures and processes are met before, during and after the subject has been seen. Items listed on these checklists include informed consent obtained, consent questions answered (and by whom), vitals recorded, medications reviewed, MR safety form, etc. These checklists are reviewed by the study coordinator and are signed off for each study subject by the coordinator monitoring the study to ensure that protocols are followed accurately and include limited variance from protocol.
- Safety monitoring – The safety monitoring of subjects enrolled in the research includes both internal and external safety checks governing the administration of ¹⁸F-DCFPyL. Internal monitoring is performed by co-investigators and external monitoring by a team of four physicians with the appropriate broad clinical and technical. The internal monitoring plan includes a brief review of each subject visit after it occurs. In this regard, the study team will discuss data quality, ¹⁸F-DCFPyL production and administration, and subject compliance and tolerance of research procedures.

The external monitoring plan will be coordinated by the Department of Radiology Medical Imaging Research Support (MIRS) administrative team. MIRS is a working group that provides investigators with the support needed to conduct clinical research that uses imaging as an outcome measure. Members include a core administrative group

(physicians, scientists, imaging modality managers, regulatory and administrative support) and ad hoc members recruited when their expertise is required for the review/monitoring of a research project. MIRS administrative team in addition to a 4-person committee of physicians/scientists will meet annually with representatives from the research team, to discuss research progress, AE/SAE reports, as well as other data reports compiled by the study team. If an AE/SAE occurs, an ad hoc committee meeting will be organized to discuss whether the event is considered serious, whether it can be attributed to research procedures, whether it constitutes non-compliance on the part of the study team, and the plan for resolution and a future remediation plan.

As part of this plan, the monitor(s) will verify that:

- The rights and well-being of human subjects are protected
- Reported study data are accurate, complete, and verifiable from source documents
- The conduct of the study is in compliance with the currently approved protocol, GCPs, applicable regulatory requirements, and guidelines for clinical research studies at the University of Wisconsin-Madison and its affiliates

10.0 STATISTICAL CONSIDERATIONS

The goals of this study are to 1) record the normal distribution of PSMA in the body, 2) record the frequency that the normal fallopian tubes and ovarian are seen on high resolution MR imaging, 3) record the distribution of PSMA in cancer tissue, and 4) estimate the sensitivity, specificity, and accuracy of PSMA PET and MR imaging.

12 healthy controls and 40 subjects with known gynecologic cancer will be enrolled in this pilot study. With final IHC staining as the “gold standard” in detection of cancer, we will estimate the sensitivity, specificity, and accuracy of PSMA PET and MR imaging. The sample size was chosen based on logistical and financial considerations. The table below shows the precision with which we will be able to estimate the sensitivity and specificity of PSMA PET and MR imaging.

| Sensitivity/Specificity | Width of 95% CI |
|-------------------------|-----------------|
| 65% | 31.1% |
| 70% | 29.9% |
| 72.5% | 29.3% |
| 75% | 28.5% |
| 77.5% | 27.7% |
| 80% | 26.5% |
| 82.5% | 25.5% |
| 85% | 24.1% |

Based on this pilot study, we plan to pursue further evaluation in larger, more appropriately powered studies if sensitivity and specificity are at least 80%.

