2.0 INTRODUCTION

Background:

The detection and distribution of cancer prior to definitive treatment is the standard of care currently [1]. Imaging plays a crucial role in this process of identifying possible areas of tumor prior to initiation of treatment [2]. Currently, imaging techniques used in clinical practice to visualize cancer mainly involve basic cross sectional anatomical imaging with or without intravenous contrast administration. These imaging techniques are limited by only providing “anatomical” information, and the diagnosis of cancer and normal tissue is partly determined by the location of the tissue. Imaging contrast agents can help visualize abnormalities, but currently cannot differentiate between malignant, inflammatory or fibrotic (scar) tissues. There have been major research advancements in functional imaging, which allow the physician to determine better what type of tissue is present in an anatomical location. Advanced PET and MR imaging techniques can evaluate the chemical composition and metabolic activity of different tissues [3, 4]. MR imaging can depict the composition of tissue (water, fat, blood and cellular) by imaging the molecules in the human body. PET imaging can depict whether or not tissue is metabolically active by imaging the injectable metabolic tracer which is taken up by different area or tissue types in the body. Knowing both the composition of the tissue and the metabolic fingerprint can help differentiate more accurately between non-cancerous and cancerous tissue types [5]. This in turns allows for more accurate cancer screening and pre-treatment staging, both which have been shown to improve outcomes in gynecologic cancer patients [1, 6]. ¹⁸F-FDG PET imaging is widely used for cancer detection and staging, but can be limited due to nonspecific uptake at sites of inflammation. A more specific PET imaging agent for more specific tumor detection, particularly in gynecologic malignancy, would help meet an unmet clinical need.

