3.0 STUDY AIMS/STUDY OBJECTIVES

The primary outcome of this research is to evaluate whether a novel imaging approach using PSMA-based ¹⁸F-DCFPyL PET and MR imaging can accurately determine the presence or absence of cancer, the accurate distribution of cancer and the normal biodistribution of PSMA in the abdomen and pelvis on PET imaging. The reference standard for the PSMA localization in cancerous tissue will be histologic and immunologic correlation on the pathologic specimens obtained at the time of standard of care surgical resection for treatment of the gynecological cancer. Specific aims for this research include the following:

1. To establish the biodistribution and radiodosimetry of PSMA-based ¹⁸F-DCFPyL on PET imaging in normal female controls and in females with known or suspected cancer.
2. To determine the sensitivity, specificity, and accuracy values of PSMA-based ¹⁸F-DCFPyL PET and MR imaging in the detection of cancer in women with known or suspected gynecologic malignancy and differentiating cancerous tissue from non-cancerous tissue. The performance of PSMA-based ¹⁸F-DCFPyL PET imaging in the detection and localization of cancerous and non-cancerous tissue will be compared to the final surgical pathology reports and to the histological and immunostaining for PSMA positive cancerous tissue on pathology.
3. To determine the most accurate approach in assessing disease burden and location, assessment of tumor burden on both the PSMA-based ¹⁸F-DCFPyL PET and MR imaging

together, and then each modality separately will be performed and sensitivity, specificity, and accuracy values will be calculated.

4.0 RESEARCH DESIGN AND METHODS:

Subject population

Fifty-two subjects will be enrolled in this research, 12 healthy controls and 40 patients with known or suspected gynecologic cancer. Up to 6 subjects will be used for the dosimetry portion. Eligibility requirements include the following:

Inclusion Criteria for healthy female controls N=12 (includes up to 6 Dosimetry subjects)

1. Women with no suspected gynecological cancer
2. No contraindications for MR or PET imaging
3. Greater than or equal to 18 years of age
4. Scheduled to undergo a hysterectomy and/or salpingo-oophorectomy

Inclusion Criteria for female controls (Dosimetry)

1. Women with or without suspected gynecological cancer
2. No contraindications for MR or PET imaging
3. Greater than or equal to 18 years of age

Inclusion Criteria for gynecologic cancer patients N=40

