1. Women with known or suspected gynecological cancer
2. No contraindications for MR or PET imaging.
3. Greater than or equal to 18 years
4. Have had or are scheduled to undergo a hysterectomy and/or salpingo-oophorectomy

Exclusion Criteria

1. Women that are pregnant or breast-feeding.
2. Age <18
3. Inability to provide informed consent on their own behalf
4. Severe kidney dysfunction (GFR <30 mL/min/1.73m²)

Subject identification and recruitment

Healthy controls will be recruited from UWHC OB/Gyn and Women's Health and PATHS clinics through referrals and from posted flyers. Healthy controls may also be recruited from the Department of Radiology Volunteer Database (2017-0004). Potential subjects will either be introduced to the research by someone involved in their care or they will be required to contact

the study team by phone or email. Those interested in participating will be scheduled for an initial visit to learn more about participation and to complete the informed consent process.

Gynecologic Oncology staff will identify cancer patients who meet the eligibility criteria and will introduce them to this research opportunity. Those interested will be referred to a study team member who will review the purpose of the research as well as details about participation.

Informed Consent and Subject Information

The consent process will occur either on a day prior to or on the day of but prior to the administration of research procedures. During the COVID-19 pandemic, consent procedures will be conducted by phone to minimize face-to-face contact subjects have with the research team. An encrypted copy of the consent form will be mailed or emailed to subjects prior to the scheduled consent phone call. A study team member will call potential subjects at the scheduled time to review the information in the consent form including study procedures, risks associated with participation, alternatives to participation and whom to contact for additional information. Any questions will be addressed during the course of the phone call and subjects will be encouraged to contact the study team with any questions or concerns they might have at any time. Upon completion of the consent process, subjects will be asked to return a copy of the signed consent form by either scanning the entire document and email back to the study team member or taking a photo of the signature page and emailing a copy to the study team member.

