- Blood will be counted on a gamma counter after dilution to determine radioactivity on the same day as the scan. After radioactive decay overnight, blood will be disposed of as per routine biohazard.

Non-dosimetry subjects: An IV will be placed to allow injection of the PET tracer, MR gadolinium agent, and glucagon (if needed) during the exams. A less than 9 mCi dose of ¹⁸F-DCFPyL radiotracer will be administered by slow IV push outside the scanner, after which, the subject will be required to sit quietly for 60 minutes to allow for adequate biodistribution of the tracer. The subjects will then be placed in the PET/MR scanner and will remain in the scanner for up to 90 minutes. After which, the whole body (defined in this protocol as base-of-skull to mid-thigh) PET and MR images will be obtained to include images post-intravenous gadolinium contrast. Glucagon (0.5mg-1mg, IV) may be administered by IV prior to the MR imaging if excessive bowel movement is seen on initial images. Glucagon is known to diminish bowel motion and improve MR image quality.

Aims 2 & 3. Sensitivity, specificity, and accuracy values of PSMA-based ¹⁸F-DCFPyL PET and MR imaging and assessment of tumor burden (40 subjects with known or suspected gynecological cancer).

This research visit is estimated to take 2-3 hours. For subjects with gynecologic cancer, the subjects will be in the scanner for up to 90 minutes. The remainder of the time will be preparatory for the scanning. An IV will be placed to allow injection of the PET tracer, MR gadolinium agent, and glucagon (if needed) during the exams. Subjects will be asked to fast for 4 to 6 hours prior to the research visit and to stay well hydrated. There will be a 1-hour uptake period after IV administration of less than 9 mCi of ¹⁸F-DCFPyL radiotracer by slow IV push. After which, the whole body (defined in this protocol as base-of-skull to mid-thigh) PET and MR images will be obtained to include images post-intravenous gadolinium contrast. Glucagon (0.5mg-1mg, IV) may

be administered by IV prior to the MR imaging if excessive bowel movement is seen on initial images. Glucagon is known to diminish bowel motion and improve MR image quality.

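### Section 10.0 calls all 40 patients known cancers and does not say who supplies the negatives for specificity, so the 80% go rule could rest on controls outside the Aim 2 and 3 population

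*Combined protocol and SAP*

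**What the plan says.** Section 10.0 (Statistical Considerations) gives the sample as "12 healthy controls and 40 subjects with known gynecologic cancer will be enrolled in this pilot study". The next sentence announces estimates of sensitivity, specificity and accuracy against IHC staining. A table of interval widths follows, and then the rule that a larger study will be pursued if sensitivity and specificity both reach 80%. No cohort, unit of analysis or source of negatives is named.

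Elsewhere the 40 are described differently:

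- Section 4.0, sample: "Fifty-two subjects will be enrolled in this research, 12 healthy controls and 40 patients with known or suspected gynecologic cancer".
- Section 4.0, eligibility for the 40: "Women with known or suspected gynecological cancer".
- Section 5.0, heading for Aims 2 and 3: "40 subjects with known or suspected gynecological cancer". Controls are not listed there; normal controls appear under Aim 1.
- Section 3.0, Aim 2: "detection of cancer in women with known or suspected gynecologic malignancy", and also "differentiating cancerous tissue from non-cancerous tissue".

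The synopsis likewise admits known or suspected cases to the group of 40. Healthy controls are defined in Section 4.0 as "Women with no suspected gynecological cancer", and in the synopsis as women without imaging evidence of gynecological cancer.

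**The concern.** Specificity depends on who the negatives are. In the population of Aims 2 and 3, the informative negatives are suspected women found benign at surgery, or non-cancerous sites in women who do have cancer. The Introduction explains why these are the hard cases: contrast agents do not separate malignant from inflammatory or scar tissue, and FDG PET "but can be limited due to nonspecific uptake at sites of inflammation". Controls chosen because nobody suspects cancer, and on the synopsis wording because imaging shows none, are likely to be easier to call negative.

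An analyst who follows Section 10.0 as written could draw every negative from the controls, or pool them with the few benign women among the 40. The specificity half of the go rule could then be met by women outside the population that the rule is meant to inform. The table would also promise more precision for specificity than the data can give.

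**Working it through.** **1. Reproducing the table.** Inputs: the eight proportions and widths in Section 10.0, with n = 40 tried as the denominator. The exact (Clopper-Pearson) 95% limits for x positives out of n are

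L = Beta quantile(0.025; x, n − x + 1), U = Beta quantile(0.975; x + 1, n − x), width = U − L.

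| Proportion | x of 40 | Computed width | Table |
|---|---|---|---|
| 65% | 26 | 31.1 | 31.1 |
| 70% | 28 | 30.0 | 29.9 |
| 72.5% | 29 | 29.3 | 29.3 |
| 75% | 30 | 28.5 | 28.5 |
| 77.5% | 31 | 27.6 | 27.7 |
| 80% | 32 | 26.6 | 26.5 |
| 82.5% | 33 | 25.4 | 25.5 |
| 85% | 34 | 24.1 | 24.1 |

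All rows agree within 0.1 point. The Wald interval at n = 40 gives 24.8 at 80% and the Wilson interval 24.3; neither fits. The table is therefore an exact interval with 40 observations, shown under one heading for both sensitivity and specificity.

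**2. What n = 40 implies.** At patient level, positives plus negatives among the 40 sum to 40. They cannot be 40 and 40. The table therefore does not show where the negatives come from.

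**3. Width at 80% for other denominators (same formula).**

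| Negatives | Width at 80% |
|---|---|
| 12 (controls only) | 48.7 |
| 40 (the table's n) | 26.6 |
| 52 (everyone) | 23.2 |

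For n = 12, 80% is 9.6 women, so 48.7 is the formula at a non-integer count. The neighbouring attainable results are 9/12 (42.8% to 94.5%, width 51.7) and 10/12 (51.6% to 97.9%, width 46.3). The smallest result on 12 controls that meets the rule is 10/12 = 83.3%. Its probability is 0.25 if true specificity in controls is 70%, and 0.56 if it is 80%.

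If only women among the 40 count, the number of negatives is the number found benign, b, which the documents do not give. With b assumed at 5, 10 or 20, a result of exactly 80% (4/5, 8/10, 16/20) has a width of 71.1, 53.1 or 37.9 points.

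**4. Direction of a pooling effect.** Let Sc be specificity in the 12 controls and Ss specificity in the b benign women among the 40.

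Pooled specificity = (12·Sc + b·Ss)/(12 + b). Excess over Ss = 12·(Sc − Ss)/(12 + b).

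The excess is positive whenever Sc exceeds Ss, and it shrinks as b grows. Neither specificity is in the documents, so the values below are assumptions:

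| Sc | Ss | b = 8 | b = 12 | b = 20 |
|---|---|---|---|---|
| 95% | 70% | 85.0% | 82.5% | 79.4% |
| 95% | 60% | 81.0% | 77.5% | 73.1% |
| 90% | 70% | 82.0% | 80.0% | 77.5% |
| 90% | 60% | 78.0% | 75.0% | 71.3% |

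For example, (12 × 0.95 + 8 × 0.70)/20 = 17.0/20 = 85.0%. In every row Ss is below 80%, yet some pooled values reach 80% and others do not. The direction is clear; whether the rule would be passed wrongly depends on the assumptions.

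**The case against.** A reader might infer that Section 10.0 takes specificity from the healthy controls and that spectrum bias in the go decision is therefore established. The documents do not support that.

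- Section 10.0 states enrolment in one sentence and the estimates in the next. It never says that controls are the negatives.
- Section 5.0 assigns Aims 2 and 3 to the 40 alone, and eligibility admits suspected cases, so benign women can be negatives within that group. Known in Section 10.0 is one discordant word.
- The table was computed with 40, not with 12 or 52.
- Negatives may be sites. Aim 2 includes separating tissue types, Section 5.0 plans staining of named sites, and the synopsis models data points clustered within patients. Non-cancerous sites inside cancer patients would then count.
- Controls outside the dosimetry group are scheduled for hysterectomy or salpingo-oophorectomy for unstated reasons, so some may have benign disease and not be easy negatives.
- The Section 10.0 rule needs sensitivity as well, so specificity alone cannot trigger it. The synopsis gives a different rule, based on disagreement with IHC. This is also a pilot without formal hypothesis tests.

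All of this stands, and it rules out calling the bias demonstrated. It does not supply a definition. Section 10.0 sets its go rule without carrying over the cohort in Section 5.0 or the unit in the synopsis, so an analyst could still pool the controls.

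**Conclusion.** The point holds as an inconsistency plus an undefined specificity denominator, with a possible upward bias of unknown size. Known in Section 10.0 conflicts with known or suspected in the synopsis, Section 4.0 and Section 5.0. The negatives behind the 80% rule are not specified. The tabulated precision for specificity cannot be obtained at patient level from the 40 women: with 12 negatives the width at 80% is 48.7 points, not 26.5.

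The 12-negative figure assumes analysis by patient, every woman with known cancer counted as reference-positive, and all 12 controls usable. The last may fail: up to 6 of the 12 may be dosimetry subjects, whose own criteria require no surgery and allow suspected cancer, so some may have no tissue reference. With 6 usable controls, 5/6 has an exact interval of 35.9% to 99.6%.

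Any figure for the inflation itself needs specificities by subgroup and a benign rate that the documents do not give.

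**What to change.** In Section 10.0:

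1. Describe the 40 as having known or suspected cancer, as the other sections do.
2. State the unit of analysis. If it is the site, account for clustering within patient, as the synopsis model already does.
3. Base sensitivity, specificity, accuracy and the Section 10.0 go rule on the Aim 2 and 3 cohort. Define negatives as women or sites confirmed non-cancerous at surgery.
4. Report the false-positive rate in controls separately, and keep it out of specificity and accuracy.
5. Restate specificity precision for the expected number of negatives, giving a range if the benign rate among suspected women is uncertain.

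The cost goes a little beyond wording. Leaving the controls out reduces the number of negatives and widens the specificity interval, perhaps greatly if few suspected women prove benign and the analysis is by patient. No extra subjects or procedures are needed.

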| Exclusion Criteria | 
 • Women that are pregnant or breast feeding. • Age <18 |

| | |
|----------------------------|--|
| | 
 • Severe kidney dysfunction (GFR <30 mL/min/1.73m²) |
| Treatment Description | ¹⁸ F-DCFPyL whole body PET/CT or PET/MR scan |
| Study Procedures | 
 • ¹⁸F-DCFPyL whole body PET/CT imaging for dosimetry studies; PET/MR scan to achieve other aims • Review of relevant imaging and medical record information |
| Statistical Considerations | 
There are no formal hypothesis tests planned.
 
Our primary goals are to:
 
 1. Record the normal biodistribution and radiodosimetry of PSMA in the body 2. Record the frequency the normal fallopian tubes and ovarian are seen on high resolution MR imaging. 3. Record the distribution of PSMA in cancer tissue 4. Estimate the frequency with which PSMA PET and MR imaging and final IHC staining disagree in their classifications of presence of disease. We will classify each data point as either an agreement or disagreement between imaging findings and IHC staining. The proportion of disagreements across all time points will be estimated with an intercept-only GEE regression model that accounts for correlation among measures from the same patient. This proportion will be reported with a 95% confidence interval. The lower bound of this confidence interval will be used to help us decide whether this approach is worthy of future study. Based on this pilot study we plan to pursue further evaluation in larger more appropriately powered studies if the lower bound of the confidence interval excludes 20%, which is chosen as a guideline to determine whether the method shows promise. |

SCHEMATIC OF STUDY DESIGN

Subject Populations

1.0 PROJECT SUMMARY:

The purpose of our proposal is to use PSMA PET and multi-parametric MR imaging, to detect the presence of gynecological cancer cells in the body. Imaging evaluation would include the appearance of normal ovaries/fallopian tubes, and cancerous tissue on different MR sequences and the distribution of PSMA in normal and pathological tissues on PET images. To determine the accuracy of the PSMA PET imaging localization in malignant tissues, PSMA staining of surgical pathology specimens will be used as the reference standard.

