PSMA, also known as folate hydrolase 1 andglutamate carboxypeptidase II, is an enzyme associated with prostate cancer but has been also found to be expressed in the tumor neovasculature of many different types of non-prostate cancer tumors [7, 8]. The PSMA molecule can be bound to a PET radionuclide as an imaging agent, specifically, ¹⁸F-DCFPyL, and this agent can be detected non-invasively using PET imaging. PSMA-based ¹⁸F-DCFPyL PET demonstrates very high tumor-to-background ratio when studied in other tumors, including prostate tumors [9]. In prostate cancer, the agent has been shown to improve detection of prostate tumors and the amount of tumor present throughout the body (tumor burden). Similar high tumor-to-background uptake of PSMA-based PET imaging has been demonstrated targeting the tumor

neovasculature of non-prostate solid tumors (example: renal cell carcinoma and lung) with potential improved tumor specificity [10, 11]. There is growing evidence in the literature which demonstrates that correctly identifying the tumor burden allows the treating physician to tailor the treatment more specifically to the individual patient to assure all the cancer cells are treated [12]. Recently, an immunohistologic pathology study demonstrated PSMA is highly and specifically expressed in the tumor vasculature of ovarian and uterine tumor specimens [9]. This makes exploring PSMA as a potential functional imaging agent for ovarian cancer very intriguing.

MR imaging is a highly sensitive and specific imaging modality that can be used for gynecologic cancers. MR images can be obtained in conjunction with PSMA PET, adding additional anatomic and multi-parametric MRI information without the need for a second imaging appointment. Emerging data demonstrates that the inclusion of functional MR sequences, specifically diffusion weighted sequences, increases the sensitive and specificity of MR imaging in the detection of tumors, including metastatic cancer deposits [3, 5].

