The overarching goals of this pilot study are to determine if imaging can depict PSMA ¹⁸F-DCFPyL uptake in gynecological cancers seen on MR imaging, and to correlate both the PSMA PET and MR imaging with histological and immunologic staining of resected tumor specimens in women undergoing the standard of care surgical treatment of their gynecological cancers. If it is possible to see PSMA on acquired images, PSMA ¹⁸F-DCFPyL could potentially be used for both screening and pre-treatment assessment of women with gynecologic cancers with improved sensitivity and specificity.

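### Section 10 scores imaging for cancer against IHC alone while Aim 2 and Section 5 also use surgical pathology, and no rule covers cancer that is PSMA-negative on staining

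*Combined protocol and SAP*

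**What the plan says.** Two places use IHC alone to decide whether cancer is present.

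- Section 10.0, on PSMA PET and MR imaging: "With final IHC staining as the “gold standard” in detection of cancer, we will estimate the sensitivity, specificity, and accuracy". The 80% sensitivity and specificity go rule closes the same section.
- Synopsis, Statistical Considerations, goal 4: "Estimate the frequency with which PSMA PET and MR imaging and final IHC staining disagree in their classifications of presence of disease". A different go rule follows there, based on whether the lower confidence bound for the disagreement proportion excludes 20%.

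Other places use pathology as well, or give the stain a narrower role.

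- Section 1.0 names the stain as PSMA and ties it to PET localization in tissue already called malignant: "accuracy of the PSMA PET imaging localization in malignant tissues, PSMA staining of surgical pathology specimens will be used as the reference standard".
- Section 3.0, lead paragraph: "The reference standard for the PSMA localization in cancerous tissue will be histologic and immunologic correlation on the pathologic specimens".
- Section 3.0, Aim 2 is where sensitivity, specificity and accuracy are set as an aim. It says that PET performance "will be compared to the final surgical pathology reports and to the histological and immunostaining for PSMA positive cancerous tissue on pathology", with no order of precedence. That sentence covers PET only.
- Section 5.0, under the histopathology and image correlation heading, uses the surgical pathology report to judge whether every disease site was seen on PET and MR. PSMA staining is done on selected sites and blocks.
- Section 3.0, Aim 3 asks for sensitivity, specificity and accuracy for PET and MR together and for each separately. It names no reference.

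**The concern.** The primary outcome in Section 3.0 concerns whether imaging can determine presence or absence of cancer. PSMA staining measures whether the tracer's target is expressed, which is a different question. Stain and tracer share that target, so a cancer without PSMA tends to be negative on both, and Section 10 would score that pair as a correct negative. MR does not depend on PSMA. When MR correctly finds such a cancer, Section 10 scores an error.

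MR therefore has competing references: IHC if Section 10 is read as covering MR, and the pathology report in Section 5. The choice affects the estimates to which the 80% rule is applied and the comparison of modalities in Aim 3. If it is left open, it could be settled after the results are known.

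**Working it through.** **1. The plan's own figures.** Section 10 gives 95% CI widths of 31.1, 29.9, 29.3, 28.5, 27.7, 26.5, 25.5 and 24.1 points for sensitivity or specificity of 65% to 85%. Exact (Clopper-Pearson) widths, B(0.975; x+1, n−x) − B(0.025; x, n−x+1) with x = n × proportion and n = 40, are 31.1, 30.0, 29.3, 28.5, 27.6, 26.6, 25.4 and 24.1. All rows agree within 0.1 point, so the table is sound for 40 units. For sensitivity, those 40 are all reference-positive. If 10% of 40 cancers are PSMA-negative, IHC leaves 36 positives, and the width at 80% becomes 28.1 points.

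**2. Inputs for the illustration.**
- From Section 10: C = 40 cancers and H = 12 controls. Other sections say known or suspected cancer, so C = 40 is an upper case.
- Assumed: one result per subject; all controls IHC-negative; sensitivity s = 85% for PSMA-positive cancer and specificity p = 90% for both modalities.
- Assumed: q is the PSMA-negative share of cancers, and d is the detection rate in those cancers. MR has d = 85%. PET has d = 0% (the extreme case) or 10% (equal to its false-positive rate).

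**3. Formulas.**
- Against IHC: sensitivity = s; specificity = [Cq(1−d) + Hp] / (Cq + H).
- Against histology: sensitivity = s(1−q) + dq; specificity = p.

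PET sensitivity for cancer is overstated whenever d < s. MR specificity is understated whenever MR detects PSMA-negative cancers more often than it calls benign tissue positive.

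**4. Results at q = 10%** (36 PSMA-positive and 4 PSMA-negative cancers).
- PET sensitivity against IHC: 85.0%.
- PET sensitivity against histology, d = 0: 0.85 × 0.90 = 76.5%.
- PET sensitivity against histology, d = 10%: 0.765 + 0.10 × 0.10 = 77.5%.
- MR specificity against IHC: (4 × 0.15 + 12 × 0.90)/16 = 11.4/16 = 71.3%, against 90% by histology.

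**5. Range over q.**

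| q | PET sensitivity vs IHC | vs histology, d = 0 | vs histology, d = 10% | MR specificity vs IHC |
|---|---|---|---|---|
| 0% | 85.0% | 85.0% | 85.0% | 90.0% |
| 5% | 85.0% | 80.8% | 81.3% | 11.1/14 = 79.3% |
| 10% | 85.0% | 76.5% | 77.5% | 71.3% |
| 20% | 85.0% | 68.0% | 70.0% | 12.0/20 = 60.0% |

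The fall in MR specificity is steep because there are few controls. With 40 benign units at q = 10% it is (0.6 + 36)/44 = 83.2%.

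**6. The 80% rule for PET alone.** Sensitivity against histology falls below 80% when q exceeds 1 − 0.80/0.85 = 5.9% (d = 0), or 0.05/0.75 = 6.7% (d = 10%). If PET finds 40% of PSMA-negative cancers, the decision does not change at q = 10%: sensitivity/specificity is 85.0/82.5% against IHC and 80.5/90.0% against histology.

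**7. Ranking of PET and MR by accuracy, q = 10%.**
- Against IHC: PET (d = 0) (30.6 + 4 + 10.8)/52 = 87.3%; MR (30.6 + 0.6 + 10.8)/52 = 80.8%.
- Against histology: PET 41.4/52 = 79.6%; MR 44.8/52 = 86.2%.

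With d = 0, the order reverses only if MR sensitivity lies between 0.85 × 0.90 = 76.5% and 30.6/32 = 95.6%.

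**8. Combined read, either modality positive, independent errors, PET d = 0.**
- Specificity against histology: 0.90² = 81.0%.
- Specificity against IHC: (4 × 0.15 + 12 × 0.81)/16 = 64.5%.

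The histology figure passes 80% only if each modality's specificity is at least √0.80 = 89.4%. At 89% each it is 79.2%, and the combined read fails under both references.

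**The case against.** The strongest defence is that the plan already means histology to identify cancer and the stain to characterise it. Sections 1.0 and 3.0 attach the stain to PSMA localization within cancerous tissue, Aim 2 and Section 5 plan the pathology comparison, and the Introduction sets out to "correlate both the PSMA PET and MR imaging with histological and immunologic staining of resected tumor specimens". PSMA-negative cancers would therefore be visible in the data. Section 10 also writes only IHC, so reading it as PSMA IHC is an inference. These points stand as evidence of intent, but Section 10 and goal 4 do not carry that intent into the definition of the estimates. If another stain is meant, Section 10 still has to name it.

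The effect may also be small: the Introduction reports that "PSMA is highly and specifically expressed in the tumor vasculature of ovarian and uterine tumor specimens". This limits the size, but the sentence gives no PSMA-negative fraction.

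Three stronger readings are tempting and are not supported.

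- A reader might infer that MR has no reference at all. Section 10 can be read as naming IHC for it, and Section 5 uses pathology, so the problem is competition between references.
- A reader might infer that the go decision will be wrong or that PET and MR will swap rank. Both need assumed inputs, and steps 6 to 8 show cases where nothing changes.
- A reader might take the combined-read reversal as likely. It needs an either-positive rule that the plan does not state, independent errors, and specificity of at least about 89.4% per modality.

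**Conclusion.** The point holds as a conflict between sections, with a missing precedence rule. Confidence is high on the text: Section 10 and goal 4 use IHC alone, Aim 2 and Section 5 add pathology, Aim 3 names nothing, and the literal Section 10 rule misclassifies histology-positive, PSMA-negative cancer. The directions follow from the definitions, given that PET finds such cancers less often than PSMA-positive ones and MR finds them more often than it calls benign tissue positive.

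The sizes are illustrations only. They rest on assumed performance, an assumed PSMA-negative fraction, one result per subject and IHC-negative controls, and they vanish when that fraction is zero. This is a pilot with no hypothesis tests, so the consequence is a possibly misleading estimate and go decision. It should be fixed before the images are scored against any reference.

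**What to change.** In Section 10 and synopsis goal 4:

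1. Make histology from the final surgical pathology report the reference for cancer present or absent, for PET with MR, PET alone and MR alone.
2. State that histology-positive, PSMA-negative tissue counts as cancer, and histology-negative, PSMA-positive tissue as non-cancer.
3. Apply the 80% rule in Section 10 to that analysis, compute the disagreement proportion in goal 4 against the same reference, and reconcile the two go rules.
4. Report PET against PSMA IHC separately, as concordance with target expression.

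The cost is wording and one more tabulation. The pathology reports are already to be correlated with the images, and staining uses the same tissue blocks. Reported PET sensitivity may be lower than it would be against IHC. The change does not settle how to score unresected sites, or subjects whose surgery preceded imaging. Those need their own rule under either reference, since both depend on surgical tissue.
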